8.0 SAFETY AND ADVERSE EVENTS

8.1 Definitions

An **adverse event** (AE) is any untoward medical occurrence in a research participant administered an investigational product and which does not necessarily have a causal relationship with this treatment. An adverse event (AE) can therefore be any unfavorable and unintended sign (including an abnormal laboratory finding), symptom, or disease temporally associated with the use of a medicinal (investigational) product, whether or not related to the investigational product.

In this trial, symptoms commonly associated with smoking withdrawal (e.g., irritability, anxiety, increased appetite, restlessness, and difficulty concentrating) will not be classified as adverse events unless they exceed the expected severity or duration. These withdrawal-related symptoms will still be systematically documented and monitored using standardized measures, such as the Minnesota Nicotine Withdrawal Scale (MNWS), and assessed during study visits for safety monitoring purposes.

Serious Adverse Event

A **serious adverse event** (SAE) is any AE that is:

- Fatal.
- Life-threatening.
- Requires or prolongs hospital stay.
- Results in persistent or significant disability or incapacity.
- A congenital anomaly or birth defect; or
- An important medical event (events that may not be life threatening but are of major clinical significance, such as a drug overdose or seizure that did not result in in-patient hospitalization).

Adverse Event Collection Period

The period during which adverse events must be collected is normally defined as the period from the initiation of any research procedures to the end of the study treatment follow-up. For this clinical trial, the study treatment follow-up is defined as 30 days following the last administration of the study intervention.

Preexisting Condition

A preexisting condition is one that is present at the start of the clinical trial. A preexisting condition should be recorded as an adverse event if the frequency, intensity, or the character of the condition worsens during the study period. At screening, any clinically significant abnormality should be recorded as a preexisting condition. Throughout the clinical trial, any new clinically significant findings/abnormalities that meet the definition of an adverse event must also be recorded and documented as an adverse event.

Post-study Adverse Event

At the last scheduled visit, each participant will be asked of any subsequent event(s) that the participant believes might reasonably be related to participation in this clinical trial. The Sponsor should be notified of any death or reportable adverse event occurring at any time after a participant has discontinued or terminated participation that may reasonably be related to this clinical trial. The Sponsor should also be notified if the study team should become aware of the development of cancer or of a congenital anomaly in a subsequently conceived offspring of a participant that was involved in this clinical trial.

8.2 Recording of Adverse Events

Safety monitoring will be implemented through the documentation and monitoring of AEs and SAEs through the use of incidence tables by severity, relationship to treatment and baseline parameters. Thorough causality analyses will be undertaken, and the necessary corrective and preventive actions will be implemented as applicable. All clearly related signs, symptoms, and abnormal diagnostic procedure results will be recorded in the research record and clinical chart and assessed by the Site-PI or other study physician in a timely manner allowing sufficient time to meet required reporting timelines for SAEs if needed.

In the event of a disagreement between the Lead PI and the site-PI over the assessment of a serious adverse event, the Lead PI will defer to the judgement of the Site-PI. If there is direct documented evidence that contradicts the Site-PI, the Lead PI will ask the Site-PI to provide the details of the event for sponsor assessment within 24 hours of the request, as per CAMH institutional procedures.

8.3 Reporting of Serious Adverse Events

8.3.1 Investigator Reporting: Notifying the Sponsor

This is an investigator-initiated study; the Lead PI is the Sponsor ([name], Waypoint). Delegated study personnel will report SAEs to the Lead PI as soon as possible (within 24 hours of becoming aware of the event).

8.3.2 Investigator Reporting: Notifying the REB

The process for notification to the REB, designated by Clinical Trial Ontario, for applicable serious adverse events (SAEs) must be completed as per REB reporting requirements. SAEs and unanticipated events must be recorded and reported to the REB in accordance with the REB's reporting requirements and timelines. Copies of each report and documentation of REB notification and REB receipt/acknowledgement must be kept in the Investigator Study Binder.

8.3.3 Sponsor Reporting of Adverse Events: Notifying Health Canada

In accordance to Health Canada incident reporting for medical devices guidance, all reportable incidents are completed by the manufacturer and importer. Thus, as the study team, we will report all reportable incidences to the manufacturer and importer (Brainsway). This includes incidences where we become aware of an event that occurred with the device that is assessed to be linked to the device based on all available information and medical assessment, *and* it leads to death, serious deterioration in the state of health of the person, or potential for death or serious deterioration in health of the person.

8.3.4 Sponsor Reporting of Adverse Events: Notifying Sites

Adverse events that meet Health Canada reporting criteria must be submitted to Health Canada by the Sponsor within the required timelines. Serious adverse events that occur at external sites must be reported to the Sponsor within 24 hours of the site's awareness of the SAE. Updates to SAEs must be provided to the Sponsor as soon as possible and within 24 hours of site awareness of the update.

Adverse events which have been assessed and determined to meet the criteria for a serious unexpected adverse event will be reported on a monthly basis to all participating study sites via a monthly line listing. The line listing will include all serious unexpected adverse events that have occurred at all participating study sites. The line listing will be sent by the Sponsor to the participating study site(s) no later than 10 business days after the end of the month for which the serious unexpected adverse events are being reported. The site-PI must review and document their acknowledgement of the serious unexpected adverse events via their dated signature within a review timeline of 10 business days. The signed line listings must be filed in the site's records, and copies of signed line listings received from the participating study site(s) must be retained in the Trial Master File of the Sponsor.

8.4 Reporting of Device Deficiencies

Device deficiencies and malfunctions will be reported directly to the Manufacturer within 48 business hours. Device deficiencies will also be recorded in the Device Recall and Deficiencies Log maintained in the Investigator Binder. No information about participants will be included.

8.5 Safety Management Plan

Participant safety will be monitored as outlined in section 1.5 Risks/Benefits. Patient participants will receive full information regarding the treatment that includes known side effects of rTMS. Best practice guidelines for rTMS are now available and will be followed accordingly during this trial[62].

Criteria by which participants will be removed for safety reasons is outlined in 4.7 Participant Withdrawal Criteria.

The reporting procedure to ensure any information relevant to participant welfare is detailed in 8.2 Reporting of Adverse Events and 8.3 Reporting of Serious Adverse Events. Adverse events are monitored according to TCPS2 and Sunnybrook Health Science Centre's "Guidelines for Reporting an Internal Serious Adverse Event". Adverse events will be assessed for at each study visit after treatment start.

In the event of a suspected or confirmed breach of privacy, we will follow protocols according to the TCPS2, Ontario's Personal Health Information Protection Act (PHIPA), and Sunnybrook Health Science Centre's guideline "Privacy and security of personal health information".

In the event that the participant presents for an rTMS treatment visit and is visibly intoxicated or in withdrawal from substance use, the rTMS technician/RPN or other study staff will notify the study physician or delegate, and treatment will not be delivered on that day. Resuming treatment or withdrawal from rTMS will be at the discretion of the Lead PI and study team based on clinical assessment of risks.

In the event that the participant expresses active suicidal ideation during a study visit, such as indicated by the PHQ-9, the trained study personnel will follow existing safety escalation policies by contacting the Site-PI or delegate immediately. The Site-PI or delegate will then contact the participant for follow-up. If a participant reports feeling unsafe due to suicidal thoughts or requires medical attention, study personnel will advise to contact 911 or go to the nearest Emergency Room. All adverse events will be assessed and reported accordingly.

Depending on the current situation of the COVID-19 pandemic, or participant preference, some study procedures might be conducted virtually. Virtual assessments will include clinical rating scale assessments and self-report questionnaires and will be done via a secure video conferencing platform (Webex or Zoom) with a physician backup.

For virtual assessments, videoconferencing (e.g. Webex, Zoom) is preferred, as some of our assessments require scoring based on behavioral observation. If the participant has no access to videoconferencing, the procedures will be completed via telephone. Both videoconferencing and telephone calls will not be recorded.

Virtual Assessment Safety Plan:

Some participants may report worsening of symptoms or suicidal ideation that may pose a safety risk during virtual assessments. In addition, some participants may report adverse events that may require further investigation due to safety reasons. In such cases, the trained study personnel will follow existing safety escalation policies by contacting the Site-PI or delegate immediately. The Site-PI or delegate will then contact the participant for follow-up. If a participant reports feeling unsafe due to suicidal thoughts or requires medical attention, study personnel will advise to contact 911 or go to the nearest Emergency Room. All adverse events will be assessed and reported accordingly.

The following safety measures will be implemented for all virtual assessments over Webex or phone:

- Confirmation of an emergency contact number for the participant, and an alternate phone number to contact them if there is an emergency, or if the call/virtual session ends inadvertently
- Confirm the participant's address, and that they are in a fixed location for the duration of the call
- Confirm there is immediate access to necessary communications technology (i.e., landline or mobile device) in order to communicate with relevant research supports or emergency services in case of an emergent research situation
- Check in on participants who leave/drop off a virtual session (i.e., if there is a safety concern) by phone or separate videoconference.
- A physician backup to the study staff is available at all times

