1.5 Risks/Benefits

Risk: Several recent investigations have demonstrated that aTMS maintains a favorable safety profile similar to conventional once-daily protocols[47–49]. In a real-world study of accelerated deep TMS for major depression, no serious adverse events were observed among 111 patients receiving two to ten sessions per day[11]. Parallel evidence from a transdiagnostic review of 63 aTMS studies likewise concluded that aTMS appears to be safe and well-tolerated, with adverse event rates comparable to once-daily TMS[50].

The most serious potential adverse event with TMS is seizure. Among 1543 participants undergoing 43,873 aTMS sessions, only one seizure (0.0023%) was reported—a rate similar to or lower than that of conventional rTMS delivered once per day[50]. Notably, the patient who experienced this single event later resumed standard once-daily TMS safely and achieved remission.

Headaches are the most frequently reported side effect, and aTMS is no exception, though rates appear comparable to those in conventional once-daily rTMS. In the aTMS review, 28.4% of participants reported headaches, followed by mild, transient scalp pain or discomfort (8.3%)[50]. Similar to once-daily TMS, these effects often diminish over the first few sessions. Apart from headache and scalp discomfort, side effects such as fatigue and other adverse events remained below 10%, and dropout rates attributable to side effects were approximately 2%[50].

This underscores that intensifying the treatment schedule with multiple daily sessions does not substantially amplify risk. Overall, the safety and tolerability of aTMS are consistent with the well-established profiles observed in standard TMS protocols.

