3.2 Primary Endpoints

The overall feasibility of accelerated deep TMS (aTMS) for smoking abstinence: assessed through tolerability (frequency of side effects reported at each visit during Week 1), acceptability (self-reported ratings collected at the end of treatment), retention rate (the proportion of participants who completed the full study), and adherence rate (the proportion of completed sessions among participants who initiated treatment).

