6.0 RESEARCH PROCEDURES

6.1 Research Visits

Prescreening during initial contact through phone, email or REDcap: A delegated research staff will conduct prescreening with the participants during their initial contact call to determine their initial eligibility to be screened in the study. This consists of a set of questions regarding inclusion and exclusion criteria. During pre-screening, we will ask participants to indicate their preferred site (Waypoint or Sunnybrook).

Screening visit (SC): A delegated research staff will conduct the informed consent discussion with the patients at the beginning of the screening visit before the assessments to determine their eligibility to participate in the study (Section 6.2. Table). The informed consent process will include a short quiz of five questions to ensure that the participant understands the key information provided. This quiz will be completed after the ICF is explained and before the participant signs it. The screening visit will confirm eligibility through the eligibility checklist that also relies on administration of the TASS and FTND, and the Mini International Neuropsychiatric Interview (MINI) to screen for psychiatric diagnoses according to the DSM-5. We will also collect demographic information, medical history and current medications. The informed consent and assessments may be performed virtually, depending on the scheduling availability of study staff and the participant (refer to Sections 8.5 and 12.2).

- Informed consent (including informed consent quiz)
- Medical history for underlying diseases
- Basic demographics, such as age, sex at birth
- Mini International Neuropsychiatric Interview (MINI)
- TMS Adult Safety Screening Questionnaire (TASS)
- Smoking Contemplation Ladder
- Target Quit Day, for scheduling the week for TMS treatment[61]
- Concomitant medication log, recorded by its generic name, dosage, and dosing frequency
- Fagerstrom Test of Nicotine Dependence (FTND). The FTND is a measure of physical dependence severity.

Baseline visit (BL):

The baseline visit will consist of urine testing using point-of-care dip testing, a concomitant medication survey, and self-report questionnaires. All components of the baseline visit must be completed within 30 days prior to W1D1; otherwise, they should be reassessed.

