Participants' activities were not systematically controlled during treatment sessions or during the intersession intervals; participants were allowed to do light cognitive activities such as reading or using their computer or smartphone.

On each day of Week 1, the TCQ-SF will be administered twice to measure nicotine craving—once before and once after the aTMS treatment.

Brief counseling for smoking cessation, adapted from the Mayo Clinic's 'Smoke Free and Living It' manual, will be administered at W1D1 and W1D5. The brief counseling sessions may also be offered remotely, based on participant preference and logistical feasibility.

The first day of Week 1 (W1D1)

- Concomitant medication log, recorded by its generic name, dosage, and dosing frequency
- Timeline Follow-Back (TLFB) – Amount of cigarette used every day since the last follow-up
- Tobacco Craving Questionnaire-Short-Form (TCQ-SF), to measure smoking craving. TCQ-SF will be administered twice—once before and once after the aTMS treatment.
- Minnesota Nicotine Withdrawal Scale (MNWS), to measure the nicotine withdrawal symptoms.
- Urine drug panel
- Urine pregnancy test, if required
- Brief counseling for smoking cessation, adapted from the Mayo Clinic's 'Smoke Free and Living It' manual.
- Resting motor threshold measurement
- Accelerated deep TMS treatment
- Adverse event log

The second, third, and fourth days of Week 1 (W1D2, W1D3, W1D4)

- Concomitant medication log, recorded by its generic name, dosage, and dosing frequency
- Timeline Follow-Back (TLFB) – Amount of cigarette used every day since the last follow-up
- Tobacco Craving Questionnaire-Short-Form (TCQ-SF), to measure smoking craving. TCQ-SF will be administered twice—once before and once after the aTMS treatment.
- Minnesota Nicotine Withdrawal Scale (MNWS), to measure the nicotine withdrawal symptoms.

- Accelerated deep TMS treatment
- Adverse event log

The fifth day of Week 1 (W1D5)

At the end of Week 1 (W1D5), a urine cotinine test will be performed, alongside TLFB to determine 7-day point-prevalence abstinence.

At W1D5, for acceptability assessment, a TMS Experience Questionnaire will be administered. Participants will be asked to retrospectively rate (from 1=not at all to 5=very much so) 15 items querying their perceptions of the treatment, its side effects, and its benefits as well as their preferences regarding treatment format and logistics.

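### Section 8.1 starts adverse-event collection at the first research procedure, but 8.5 and the visit lists start it at treatment, so the Week 1 tolerability count has no structured pre-TMS side-effect reading behind it

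*Protocol*

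**What the plan says.** **Start of collection.** Protocol 8.1 (Adverse Event Collection Period) gives the usual period as "the period from the initiation of any research procedures to the end of the study treatment follow-up". It then makes only the end specific to this trial: "For this clinical trial, the study treatment follow-up is defined as 30 days following the last administration of the study intervention". No other start is put in place of the general one. Section 8.5 says: "Adverse events will be assessed for at each study visit after treatment start".

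**What is scheduled.** In 6.1, the item "Adverse event log" is absent from the screening and baseline lists. It first appears on day 1 of Week 1, as the last item, after the TMS treatment. The schedule of events in 6.2 appears to agree, as far as its layout can be read.

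**The endpoint.** Section 3.2 defines one component of the primary endpoint as "tolerability (frequency of side effects reported at each visit during Week 1". It does not limit this to new, worsened or treatment-related symptoms.

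**What is recorded before treatment.** Section 8.1 says: "At screening, any clinically significant abnormality should be recorded as a preexisting condition". A pre-existing condition then becomes an AE only if its frequency, intensity or character gets worse. Screening also includes a medical history of underlying diseases.

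**The concern.** There are two linked problems.

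First, the start of AE collection is contradictory. On the baseline visit, 6.1 says: "All components of the baseline visit must be completed within 30 days prior to W1D1". Up to 30 days can therefore pass between baseline and the first session, and more from screening. Under 8.1 that interval lies inside the collection period; under 8.5 no assessment is scheduled in it. Section 3.1 also expects some enrolled participants never to start TMS. They fall inside the 8.1 period but have no scheduled AE assessment at all.

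Second, the symptoms that 1.5 expects from TMS (headache, scalp discomfort, fatigue) are everyday ones. With no control arm, a participant's own state before the first session is the only within-trial reference for them. If it is not recorded, an existing mild headache reported in Week 1 cannot be told from a new one. The trial is meant to guide a later controlled study, and this reading cannot be recovered once treatment has begun.

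**Working it through.** The protocol states no tolerability threshold, test or power figure, so there is no planned number to reproduce. The check sets the sections side by side.

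1. **Is the start date truly inconsistent?** Section 8.1 qualifies its period with the word normally, which softens it. But the next sentence adapts only the end of the period, so the general start still stands. Section 8.5 and the 6.1 visit lists start later. The texts do not agree.

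2. **Is there any structured side-effect reading before TMS?** The baseline visit in 6.1 has urine tests, a concomitant medication survey and questionnaires on smoking, dependence, craving, withdrawal, depression, anxiety and mania. The protocol describes none of these as measuring headache or scalp discomfort. The day 1 AE log is listed after treatment, and nothing says that it is completed beforehand. By contrast, craving is scheduled before and after treatment on every Week 1 day, so a pre-session reading fits the visit.

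3. **Does the worsening rule fill the gap?** It needs an earlier record of how frequent or intense the symptom was. The only such record that 8.1 requires is of clinically significant abnormalities at screening. An occasional mild headache may well not qualify.

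4. **Does the causality review fill it?** Section 8.2 tabulates AEs by relationship to treatment and by baseline parameters. That removes part of the background from the safety tables. Section 3.2 does not apply it to tolerability, and for a mild symptom the open-label judgement would be made without a structured earlier reading.

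5. **What would one misclassified participant do?** Take tolerability as a proportion of treated participants (an assumption; 3.2 says only frequency). One participant whose pre-existing symptom is counted adds 1/40 = 2.5 percentage points if all 40 are treated, or 1/30 = 3.3 points if 30 are.

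6. **How precise is the proportion anyway?** Section 1.5 cites, for accelerated TMS, that "28.4% of participants reported headaches". At n = 40, 0.284 × 40 = 11.4, so about 11/40 = 27.5%, with an exact (Clopper-Pearson) 95% interval of 14.6% to 43.9%. At n = 30, 0.284 × 30 = 8.5, so about 9/30 = 30.0%, with an interval of 14.7% to 49.4%. A few misclassified participants would sit inside this sampling uncertainty, but they would push the estimate in one direction only.

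**The case against.** The strongest objections, and what stands of each:

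- **Aligning the dates would not change the endpoint.** Tolerability is confined to Week 1, so logging AEs from consent leaves its definition as it is. This is correct. The benefit comes from reporting new or worsened symptoms against the added readings, not from the wording change alone.
- **Section 8.1 defines an AE as occurring in a participant who has received the investigational product, so a log that starts at treatment fits.** This is a fair reading, but it puts 8.1 at odds with its own collection period, which is a further reason to reconcile the text.
- **The protocol already removes background symptoms.** It does so in part, through the worsening rule, the causality tables, and the rule that expected withdrawal symptoms are not AEs and are followed with a withdrawal scale. A reader might infer that every background headache will be counted as a TMS side effect. The documents do not support that. The gap is limited to mild symptoms with no screening record. The withdrawal examples in 8.1 name neither headache nor fatigue.
- **Readings before treatment cannot deal with the quit week.** This stands. Section 5.1 sets the target quit date to coincide with the first TMS day, allowing for scheduling. A headache that first appears on day 2 or 3 because of quitting would still count as new.
- **A crude frequency is what compares with the cited 28.4%.** This also stands, and is a reason to keep the crude figure.

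A reader might also try to size the bias by adding an assumed background headache rate to 28.4%. That does not work. The 28.4% is a reported rate that may already contain background headaches, and the protocol gives no background rate to add.

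**Conclusion.** The concern holds in a limited form. The start of AE collection in 8.1 conflicts with 8.5 and the 6.1 visit lists, and apparently with the 6.2 schedule; these must be reconciled. No structured side-effect reading is scheduled before the first TMS session. The Week 1 tolerability count may therefore include mild pre-existing headache, fatigue or scalp discomfort, because the worsening rule has nothing to compare them with unless they were clinically significant at screening.

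The bias, if any, is upward. Its size cannot be computed from the documents. The 2.5 to 3.3 points per affected participant assume a per-participant proportion with 40 or 30 treated, and say nothing about how many would be affected. The conclusion also assumes that the side-effect count is taken from the AE log as scheduled, and that no separate pre-treatment symptom form exists outside the protocol. No sample-size or abstinence figure is touched. This is a modest but worthwhile correction to a primary-endpoint component, and it has to be made before enrolment to be of use.

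**What to change.** 1. Reconcile 8.1, 8.5, the visit lists in 6.1 and the schedule in 6.2 on one start for AE collection. State what applies to enrolled participants who never start TMS.
2. Administer the AE/side-effect log at the baseline visit, and again on day 1 of Week 1 before the first session.
3. In 3.2, report Week 1 tolerability as symptoms that are new or worsened relative to those readings. Report the crude frequency alongside it, so that the result stays comparable with the rate cited in 1.5.
4. State in the report that this removes pre-existing symptoms only, and that effects of TMS and of quitting during Week 1 remain mixed.

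The cost is one short form at two visits that already take place, plus wording changes. Sample size and visit count stay the same.
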